### **6.3.2.11. Part 2 (Dose Expansion), End-of-treatment (Post-cycle)**

This EOT visit should occur at the earliest day possible within 30 days after the last administration of DS-3201b, but before beginning any other form of anticancer therapy.

The following assessments will be performed at this visit:

- Perform a complete physical examination and record weight and height.
- Obtain vital sign measurements (systolic and diastolic blood pressure, pulse rate, respiratory rate, and body temperature).
- Assess functional status using the ECOG-PS Scale (Section [17.1](#)).
- Obtain blood samples for clinical laboratories (Section [9.7](#)).
- Obtain a serum or urine sample for pregnancy testing in women of childbearing potential.
- Obtain a blood sample for biomarkers.
- Obtain a blood sample for DS-3201a PK measurement.
- Obtain a blood sample for protein binding determination.
- Obtain a urine sample for urinalysis (Section [9.7](#)).
- Perform a 12-lead ECG in triplicate (5 minutes apart).
- Record concomitant medications.
- Assess subjects for AEs.
- Review pill diary to assess treatment compliance.
- Review of returned study medication and assessment of compliance.
- Record reason for treatment discontinuation.
- Bone marrow re-biopsy (optional) for subjects who achieved an initial CR/PR to DS-3201b but later developed progressive disease while on therapy (Section [6.3.1.12](#)).

### **6.3.2.12. Part 2 (Dose Expansion) End-of-study Follow-up**

The EOS Follow-up should occur 30 ( $\pm$  5) days after the last administration of DS-3201b. Follow-up information will be collected via a phone call or site visit. If the subject begins

another form of anticancer therapy before the end of the 30 ( $\pm 5$ )-day period, every effort will be made to complete all the EOS assessments prior to commencing the new therapy. The Investigator should follow subjects with AEs until the event has resolved or the condition has stabilized. In case of unresolved AEs, including significant abnormal clinical laboratory values at the EOT assessment, these events will be followed-up until resolution or until they become clinically not relevant.

The following information will be collected at this follow-up:

- Assessment of AEs
- Current medications
- Subject survival status
- Collection of any empty bottle(s) along with any unused medication

If the EOS Follow-up is not performed (ie, due to death, lost to follow-up, etc.), record the reason.

#### **6.3.2.13. Part 2 (Dose Expansion) Bone Marrow Re-biopsy**

Please see Section [6.3.1.12](#) for details regarding performing bone marrow re-biopsy in Part 2.

### **6.4. Long-term Follow-up**

After completion of the EOS follow-up visit (30 [ $\pm 5$ ] day safety, Section [6.3.1.11](#) and Section [6.3.2.12](#)), subjects will then enter the LTFU Period, during which they will be followed every 3 months for collection of information on subsequent AML/ALL treatment (including stem cell transplants), HCT and HCT-relevant information (if performed), response to treatment, and survival, including the cause and date of death. LTFU will continue until death, loss to follow-up, or until the Sponsor terminates the study. These visits will be conducted via telephone.

If direct contacts are not possible or if LTFU is not performed due to withdrawal of consent, subject refusal to participate in LTFU, or loss to follow-up, the site must make every effort to collect survival status from public records (eg, death certificates) in accordance with local laws and document as best possible the specific reason for inability to collect LTFU data.

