DS-3201b-related histopathological findings were noted in similar tissues in both rats and dogs. These changes primarily included bone marrow hypocellularity, atrophy and depletion of lymphoreticular tissues, and glandular mucosal degeneration of the gastrointestinal tract that was associated with mononuclear cell inflammation. Tubular degeneration of the kidney was also noted in both species. In the rat DRF study, there was vacuolation and/or infiltration of foam cells in many organs suggestive of a drug-induced phospholipidosis (PLD). All findings in surviving animals in both the rat and dog 4-week GLP studies reversed after a 4-week recovery period. Based on these findings, the severely toxic dose in 10% of animals (STD10) in rats was 200 mg/kg/day and the highest non-severely toxic dose (HNSTD) in dogs was 30 mg/kg/day.

In the 13-week GLP toxicity study in rats, DS-3201b was given to rats (15/sex/group plus 3/sex/group for TK analysis) at doses of 0 (vehicle), 20, 60, and 200 mg/kg/day once daily for 13 weeks by oral administration. Five rats/sex/group remained on a 4-week recovery period to assess reversibility of DS-3201b effects. The histopathological examination of the recovery groups is ongoing. Preliminary results from the ongoing 3-month toxicity study in rats showed the potential risk of developing lymphoid malignancies during long-term administration of DS-3201b. However, no similar findings were noted in other animal 3-month toxicity studies of DS-3201b. Additionally, there have been no reports related to this new toxicity finding in subjects currently enrolled in any of the ongoing trials. Careful monitoring is mandated to maintain an acceptable benefit-risk balance as observed in the current and future study subjects.

Preliminary results from an ongoing 3-month toxicology study in dogs suggested a potential for scrotal swelling in males administered DS-3201b. Although the scrotal lesions appear to be a new finding, this is not expected to significantly impact the on-going clinical studies since these effects can be monitored and are reversible with discontinuation of dosing. The significance of this finding is unknown at this time, but the Sponsor will continue to monitor similar events during the course of the ongoing study.

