In view of the results of 4-week repeated-dose toxicity studies in rats and dogs, potential target organs of DS-3201b were suggested to be the kidney (tubular degeneration), gastrointestinal tract (increased inflammatory infiltrate and mucosal degeneration), lymphoid organs (eg, decrease in WBC count, thymic atrophy, hypocellularity of bone marrow), and hematopoietic system (eg, changes in RBC parameters, platelets, and reticulocytes). There were effects on the clotting system in rats, whereas there was evidence of increased histamine levels with associated clinical signs in dogs. In terms of the cardiovascular effects, an increase in QTc interval was observed in 4-week repeated-dose toxicity and safety pharmacology studies in dogs.

In the 13-week GLP toxicity study in rats, malignant lymphoma was observed in the thymus and had metastasized to multiple organs. Increased cellularity, suggestive of a hyperplastic condition, was also observed. The new findings from the GLP toxicity study suggest a potential risk of the development of lymphoid malignancies in humans. No similar findings were noted in the 3-month toxicity study of DS 3201b in dogs. T-cell lymphomas have been observed in animals treated with DS-3201b (an EZH1/2-inhibitor) in repeat dose toxicology studies. This has also been observed in tazemetostat (an EZH2-inhibitor).

Secondary malignancies, including malignant lymphoma, have not been reported from DS-3201b studies. However, the treatment of patients with tazemetostat has been seen to increase the risk of developing a secondary T-cell malignancy, where a pediatric patient treated with tazemetostat developed a secondary T-cell lymphoblastic lymphoma after approximately 15 months of therapy. The dose or duration of therapy at which EZH2 inhibition and/or EZH1/2 inhibition do not increase the risk of a secondary lymphoid malignancy is unknown.

Preliminary results from an ongoing 3-month toxicology study in dogs suggested a potential for scrotal swelling in males administered DS-3201b. Although the scrotal lesions appear to be a new finding, this is not expected to significantly impact the ongoing clinical studies since these effects can be monitored, and are reversible with discontinuation of dosing. The significance of this finding is unknown at this time, but the Sponsor will continue to monitor similar events during the course of the ongoing study.

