## 9. SAFETY ASSESSMENTS

### 9.1. Adverse Events

All clinical AEs occurring after the subject signs the ICF and up to 30 ( $\pm 5$ ) days after the last dose of study drug during either Part 1 or Part 2, whether observed by the Investigator or reported by the subject, will be recorded on the AE eCRF page. Medical conditions (including clinical laboratory values/vital signs that are out of range) that were diagnosed or known to exist prior to informed consent will be recorded as part of medical history. All SAEs are to be reported according to the procedures in Section 9.5 SAE Reporting Procedure for Investigators. Always report diagnosis as the AE or SAE term. When a diagnosis is unavailable, report the primary sign or symptom as the AE or SAE term with additional details included in the narrative until the diagnosis becomes available. If the signs and symptoms are distinct and do not suggest a common diagnosis, report them as individual entries of AE or SAE. For events that are serious due to hospitalization, the reason for hospitalization must be reported as the SAE (diagnosis or symptom requiring hospitalization). A procedure is not an AE or SAE, but the reason for the procedure may be an AE or SAE. Pre-planned (prior to signing the ICF) procedure or treatment requiring hospitalization for pre-existing conditions which do not worsen in severity should not be reported as SAEs (see Section 9.4.2 for definitions). For deaths, the underlying or immediate cause of death should always be reported as an SAE. Disease progression is a study endpoint and, consequently, should not be reported as an AE or SAE. However, when a subject dies from disease progression with no other immediate causes, “disease progression” should be reported as an SAE. In addition, any serious, untoward event that may occur subsequent to the reporting period that the Investigator assesses as related to study drug should also be reported and managed as an SAE.

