## **9.3. Adverse Events of Special Interest**

Differentiation syndrome is an adverse event of special interest (AESI) for DS3201-A-U102 and as of 18 Jan 2020, it has been reported in 1 subject with AML.

When subjects with acute leukemia are treated with DS-3201b, vigilance should be exercised in while monitoring them for development of possible differentiation syndrome. It is important to both promptly recognize the signs and symptoms of differentiation syndrome and implement prompt management.

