#### **9.4.4. Causality Assessment**

The Investigator should assess causal relationship between an AE and DS-3201b on the basis of his/her clinical judgment and the following definitions. The causality assessment should be made based on the available information and can be updated as new information becomes available.

- 1 = Related:
  - The AE follows a reasonable temporal sequence from study drug administration, and cannot be reasonably explained by the subject’s clinical state or other factors (eg, disease under study, concurrent diseases, and concomitant medications).
  - The AE follows a reasonable temporal sequence from study drug administration, and is a known reaction to the drug under study or its chemical group, or is predicted by known pharmacology.
- 2 = Not Related:

- The AE does not follow a reasonable sequence from study drug administration, or can be reasonably explained by the subject's clinical state or other factors (eg, disease under study, concurrent diseases, and concomitant medications).

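### After about 30 days from the last dose, a non-fatal second malignancy is recorded only if serious and judged drug-related, although lymphoid malignancy is a listed important potential risk

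*Combined protocol and SAP*

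**What the plan says.** **The risk.** Section 1.4.2 includes developing lymphoid malignancy among the important potential risks. It cites malignant lymphoma in the 13-week rat study of DS-3201b. It also cites one pediatric patient on tazemetostat, an EZH2 inhibitor, who "developed a secondary T-cell lymphoblastic lymphoma after approximately 15 months of therapy". The same section states that no secondary malignancy has been reported with DS-3201b, and that the dose or duration free of this risk is not known. On the rat finding, Section 1.1.1.5.5 (Toxicology) says: "Careful monitoring is mandated to maintain an acceptable benefit-risk balance".

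**The recording window.** Under Section 9.1, all adverse events are recorded from consent until 30 (±5) days after the last dose, whatever their cause. Beyond that, what must still be reported is "any serious, untoward event that may occur subsequent to the reporting period that the Investigator assesses as related to study drug".

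**The causality rule.** Section 9.4.4 has two categories. An event can be Related because it is a recognised reaction to the drug or its chemical group, or is expected from the pharmacology. It is Not Related if it "does not follow a reasonable sequence from study drug administration, or can be reasonably explained by" the subject's condition or other factors, with the leukemia itself, other diseases and other medication as examples.

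**Long-term follow-up.** Section 6.4 says of subjects that "they will be followed every 3 months for collection of information on subsequent AML/ALL treatment (including stem cell transplants"; it adds other transplant information, response, and "survival, including the cause and date of death". The contacts are by telephone. Footnote r of Tables 17.2 and 17.3 covers treatment, transplant and response.

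**The Extension Phase.** Table 17.4 collects adverse events at each cycle and at a visit 30 to 45 days after the last dose. It has no long-term follow-up column.

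**The concern.** The protocol names a risk, calls for careful monitoring of it, and telephones every surviving subject in long-term follow-up every 3 months. None of those calls asks about it. Once the routine window closes, a second cancer that does not kill the subject reaches the database only through the investigator's causality judgement. That judgement is difficult here: a new lymphoid cancer in a heavily treated leukemia patient nearly always has another plausible explanation.

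What is at stake is how silence is read. If the report lists no late second malignancies, the reader cannot tell whether none occurred or whether the plan did not ask. Section 1.3 says the results will inform later studies and combinations, so the distinction has some use.

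**Working it through.** The documents contain no figure for this risk, so there is nothing of the plan's own to reproduce. The check is to follow a second malignancy through each period and see which rule would record it.

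| When it arises | Serious and judged related | Non-fatal, judged unrelated | Fatal |
|---|---|---|---|
| Consent to 30 (±5) days after last dose | Recorded (9.1) | Recorded (9.1) | Recorded (9.1) |
| Later, in long-term follow-up | Reported as an SAE (9.1) | **No route** | Cause of death (6.4) |
| Extension treatment, to the 30-to-45-day visit | Recorded (Table 17.4) | Recorded (Table 17.4) | Recorded (Table 17.4) |
| After that Extension visit | SAE, if the Section 9.1 rule carries over | **No route** | No route shown, unless Section 6.4 also applies |

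Three points follow.

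1. The gap is confined to non-fatal cases after the window. Seriousness is unlikely to be the obstacle, since a new cancer would usually qualify as an important medical event under Section 9.4.2. The relatedness judgement is what decides.
2. Section 9.4.4 allows either answer. The class-reaction clause points to Related, because Section 1.4.2 supplies animal lymphomas with DS-3201b and a clinical case with another inhibitor of EZH2. The alternative-explanation clause points to Not Related. The section does not say which prevails when both apply.
3. The subjects with the longest exposure are those in the Extension Phase, and for them the schedule shows no contact after the last visit.

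**How many subjects could be affected.** The inputs are the AML survival figures in Section 1.2 (median 3.8 months if refractory to induction; less than 6 months if relapsed) and the 40 subjects planned at the expansion dose in Section 11.10. Assumptions: exponential survival, S(t) = 0.5^(t/m); 6 months taken as an upper value for the median; the AML figures applied to ALL as well. At 15 months, used only as a landmark:

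- m = 3.8: 0.5^(15/3.8) = 0.065, and 40 × 0.065 = 2.6 subjects alive;
- m = 6: 0.5^(15/6) = 0.177, and 40 × 0.177 = 7.1 subjects alive.

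So about 3 to 7 of 40 would be alive at that point. This says only that long survivors will be few. Turning it into a share of follow-up time outside the window would need a treatment duration, which the documents do not give, so the calculation stops here.

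**The case against.** The strongest reply is that most of the capture is already in place. Adverse events are recorded regardless of causality throughout treatment and for about a month after, and again at every Extension cycle. Related serious events after the window must be reported; this is an instruction, with no time limit. The class-reaction clause gives a new T-cell lymphoma a direct route to Related. Cause of death is collected whatever the causality. Survival is short, and no analysis claiming absence of second malignancies is planned. All of this stands, and it narrows the point to late, non-fatal cases judged unrelated. It does not close that gap.

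A reader might infer more than the documents support:

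- **That the 15-month case shows late onset after stopping.** It concerned another drug and arose during therapy. A subject here with the same exposure would still be inside the recording window at that time.
- **That the trial will under-count, by a stated percentage.** Whether any such case will occur is unknown, and a percentage would rest on an assumed treatment duration.
- **That making malignancy an event of special interest would solve it.** Section 9.3 names differentiation syndrome and asks for vigilance and prompt management, but gives it no longer collection window.
- **That a new T-cell lymphoma will be filed as progression of T-cell ALL.** The protocol does not mention T-cell ALL as a study population, so this is conjecture.
- **That an incidence per person-year is needed.** In a small single-arm study, with later chemotherapy and transplant, it would be hard to interpret.

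**Conclusion.** The point holds in a limited form. From about 30 (±5) days after the last dose, a non-fatal second malignancy is recorded only if it is serious and judged related. The follow-up calls do not ask about it, and the Extension Phase shows no follow-up beyond its final visit. Followed as written, the plan can miss late non-fatal cases judged unrelated, for a risk that the protocol itself lists. Fatal cases may be found through cause of death.

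The size cannot be stated from the documents. The survival figures suggest that few subjects would be exposed to the gap for long; that rests on exponential survival and on AML figures applied to both diseases. The dose decisions, sample size and response analyses are unaffected. This is a cheap improvement to what the trial collects, not a flaw in its primary purpose.

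**What to change.** 1. In Section 6.4, and in footnote r of Tables 17.2 and 17.3, add an item to each 3-monthly contact: new primary malignancy, with type, date and, if available, histology. It should be asked regardless of causality and recorded separately from leukemia progression, so that it is not absorbed into the response information already collected on the same call.
2. In Section 17.9, state whether Extension Phase subjects enter the same long-term follow-up after their last visit.
3. List the cases in the safety report, with time from first and last dose and any intervening chemotherapy or transplant.

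The cost is one eCRF item and a short protocol edit. The main study needs no new visit or procedure, because the calls already take place. If Extension subjects are to be followed, they would need the same telephone contacts. The limitation to accept is that late cases arising after later chemotherapy or transplant will be hard to attribute; the listing makes them visible but does not settle causation.

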### **6.5. Protocol Deviations**

The Investigator should conduct the study in compliance with the protocol agreed to by DSI and, if required, by the regulatory authority(ies), and which was given approval/favorable opinion by the IRB.

A deviation to any protocol procedure, or waiver to any stated criteria, will not be allowed in this study except where necessary to eliminate immediate hazard(s) to the subject. DSI must be notified of all intended or unintended deviations to the protocol (eg, inclusion/exclusion criteria, dosing, missed study visits) on an expedited basis.

The Investigator, or person designated by the Investigator, should document and explain any deviation from the approved protocol.

If a subject was ineligible or received the incorrect dose or investigational treatment, and had at least one administration of investigational product, data should be collected for safety purposes.

The Investigator should notify the IRB of deviations from the protocol in accordance with local procedures.

## 7. EFFICACY ASSESSMENTS

Efficacy assessments will be based on bone marrow assessments to be performed at Screening, Cycle 1 Day 8, and every cycle of treatment (ie, at start of Cycles 2, 3, 4, etc.) while the subject remains on study drug. The clinical activity of DS-3201b will be assessed using the revised IWG response criteria for AML or the NCCN Guidelines (Version 3.2013) for ALL (Section 17.3).

The efficacy endpoints will be:

- CRc rate (CR, CRi, and CRp)
- CR
- CRi or CRp
- MLFS
- PR rate
- ORR = CRc+PR
- DOR: Time from the first objective evidence of response to the first objective evidence of disease progression
- OS: Time from the date of enrollment to the date of death from any cause
- 30- and 60-day mortality rate

## 8. PHARMACOKINETIC/PHARMACODYNAMIC ASSESSMENTS

Blood samples for DS-3201a PK analyses (eg, total and unbound concentrations) will be obtained at the time points specified in the Schedule of Events (Section 17.8) for subjects in the Dose Escalation and Dose Expansion parts of the study.

Additionally, blood samples may be obtained at any time during the study if deemed clinically necessary or when moderate or strong CYP3A and/or P-gp inhibitors are co-administered with DS-3201b. In the event of co-administration of moderate or strong CYP3A and/or P-gp inhibitors, blood samples for PK analyses (total and unbound concentrations) should be collected at the following timepoints relative to DS-3201b dosing:

- Pre-dose, 4 hours, and 8 hours post-dose of DS-3201b on the first day of CYP3A and/or P-gp inhibitor dosing
- Pre-dose, 4 hours, and 8 hours post-dose of DS-3201b within 28 days after last day of CYP3A and/or P-gp inhibitors dosing

At each time point, blood samples will be collected for analysis of total and unbound concentrations of DS-3201a.

Instructions for the handling of blood samples and shipping of plasma samples for DS-3201a PK analyses are included in a separate document (eg, laboratory manual). The actual time of study drug administration and the exact time of blood sampling for DS-3201a PK analysis must be recorded on the eCRF.

The DS-3201a PK samples will be shipped to a central laboratory for forwarding to a Sponsor -designated bioanalytical laboratory. Plasma concentrations of DS-3201a will be measured using a validated assay at the bioanalytical laboratory. Plasma metabolites of DS-3201a may also be measured based on the assay availability.

